Eligible subjects may enter the Extension Phase immediately following the completion of Visit 15 of the Core Study. Subjects who are eligible to participate in the Extension Phase but who do not transition to the Extension Phase on the day of Visit 15 may enter the Extension Phase any time within 4 weeks of Visit 15. All subjects who enter the Extension Phase will be treated with elenbecestat, including the subjects who received placebo during the Core Study. For all subjects, assessments performed at Visit 15 will serve as baseline values for the Extension Phase. (revised per Amendment 06)

An independent data safety monitoring board (DSMB) will convene at regular intervals to monitor the overall safety of the study and to make recommendations to the sponsor related to study safety as appropriate. The DSMB will be asked to review the cumulative safety data, which includes measures of cognitive safety at the group level, up to the date identified

to make a determination if the trial is safe to proceed unchanged or to provide recommendations to the sponsor as to how to proceed. (revised per Amendment 06) The study will proceed, including randomization of additional subjects, during DSMB safety reviews. Details will be provided in the DSMB Charter.

An overview of the study design is presented in [Figure 1](#).

[figure not shown]

Figure 1 Study Design for E2609-G000-301 (revised per Amendment 06)

Elenbecestat = Test drug, EoT = End of Treatment, PET = positron emission tomography, R = randomization.

- a: Subjects who participate in the optional longitudinal tau PET substudy will be permitted an additional window of up to 5 days (resulting in a total of up to 85 days) in order to accommodate the additional tau PET scan required to be performed during prerandomization. (revised per Amendment 05)
- b: The last day of the Core Study (Visit 15) is also the first day of the Extension Phase

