- q: Study-eligible subjects from select geographical sites (based on proximity to the tau PET ligand manufacturing sites) in the US who have an amyloid positive study-specific PET scan and consent to participate in the amyloid PET substudy will also be offered participation in a third optional longitudinal substudy (tau PET substudy). Tau PET scanning will be performed using a sponsor-supplied tau PET imaging agent, eg PI-2620. Participation in the tau PET substudy is optional and will require specific consent that will not affect enrollment or treatment in the main study or participation in the amyloid PET or CSF substudies. Subjects who participate in the optional longitudinal tau PET substudy will have up to 14 days to be randomized into the study from the reporting of the last screening eligibility assessment in order to accommodate the additional tau PET scan required pre-randomization. There must be at least 48 hours between the tau PET scan and randomization. If the subject has also consented to participate in the longitudinal CSF substudy, there must be at least 48 hours between each procedure (amyloid PET scan, tau PET scan and CSF collection) and between the last procedure and randomization. Only those subjects who have a study-specific amyloid positive PET scan and who have consented to both amyloid and tau PET substudies will be administered the tau PET tracer and scanned. (revised per Amendment 05)

Table 5 Schedule of Procedures/Assessments in Study E2609-G000-301 (Revised per Amendments 05 and 06)

Phase Period	Randomization												Follow-Up			UNS Visit ^d
	Treatment												ED ^b	14 ^c	15 ^c	
Visit ^a	2	3	4	5	6	7	8	9	10	11	12	13	ED ^b	14 ^c	15 ^c	
Day	1	15	29	57	85	183	274	365	456	547	638	729		757	813	
Week	1	3	5	9	13	27	40	53	66	79	92	105		109	117	
Weeks elapsed since 1st dose	0	2	4	8	12	26	39	52	65	78	91	104		108	116	
Nominal months elapsed since 1st dose	0		1	2	3	6	9	12	15	18	21	24		25	27	
Procedures/ Assessments																
Consent (subject and study partner)																X ^{dd}
Routine physical examination with dermatologic review	X	X	X	X	X	X	X	X	X	X	X	X	X	X	X ^c	X
Inclusion and Exclusion criteria	X														X ^{dd}	
Vital signs and respiratory rate ^f	X	X	X	X	X	X	X	X	X	X	X	X	X	X	X ^c	X
Weight	X				X	X	X	X	X	X	X	X	X		X	X
Neurologic examination ^g					X	X		X		X		X	X		X	X
Concomitant medications ^h	X	X	X	X	X	X	X	X	X	X	X	X	X	X	X	X
Single 12-lead ECG ⁱ	X		X		X	X		X		X		X	X	X	X ^c	X

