Blood samples for PK ^w		X	X		X	X		X		X		X	X			
Blood samples for PD and exploratory biomarkers ^x	X	X	X		X	X		X		X		X	X	X	X	
CSF sampling for PK and PD (optional substudy) ^y												X	X		X ^{cc}	
Adverse events ^{ff}	X	X	X	X	X	X	X	X	X	X	X	X	X	X	X	X
Sleep/Dream Questionnaire ^z	X	X	X	X	X	X	X	X	X	X	X	X	X	X	X	X
Possible Drug Abuse Potential Form/ Questionnaire ^{aa}	X	X	X	X	X	X	X	X	X	X	X	X	X	X	X	X
Randomization	X															
Dispense study drug	X ^b b	X	X	X	X	X	X	X	X	X	X				X ^{dd}	

Table 5 Schedule of Procedures/Assessments in Study E2609-G000-301 (Revised per Amendments 05 and 06)

Phase	Randomization														
	Treatment												Follow-Up		
Period	2	3	4	5	6	7	8	9	10	11	12	13	ED ^b	14 ^c	15 ^c
Visit ^a															
Day	1	15	29	57	85	183	274	365	456	547	638	729		757	813
Week	1	3	5	9	13	27	40	53	66	79	92	105		109	117
Weeks elapsed since 1st dose	0	2	4	8	12	26	39	52	65	78	91	104		108	116
Nominal months elapsed since 1st dose	0		1	2	3	6	9	12	15	18	21	24		25	27
Procedures/ Assessments															

Notes:

ADAS-cog14 = Alzheimer’s Disease Assessment Scale - Cognitive subscale (14 items), AE = adverse event, CBP = child-bearing potential, CDR = Clinical Dementia Rating scale, CMV = cytomegalovirus, CNS = central nervous system, CSF = cerebrospinal fluid, C-SSRS = Columbia Suicide Severity Rating Scale, ED = Early Discontinuation, EQ-5D = EuroQol-5 Dimensions, FAQ = Functional Assessment Questionnaire (also known as the Functional Activities Questionnaire), fMRI = functional MRI (to be performed task free at resting state), HSV1 = herpes simplex virus 1 (orolabial herpes), HSV2 = herpes simplex virus 2 (genital herpes), INR = International Normalized Ratio, LP = lumbar puncture, MMSE = Mini Mental State Examination, MRI = magnetic resonance imaging, NPI = Neuropsychiatric Inventory, PBMC = peripheral blood mononuclear cell, PD = pharmacodynamics, PET = positron emission tomography, PK = pharmacokinetics, QOL-AD = Quality of Life in Alzheimer’s Disease, QTcF = QTc interval calculated using Fridericia’s formula, UNS = unscheduled, vMRI = volumetric MRI.

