reported during the first 4 weeks following the last dose of study drug that might indicate physical dependency also require a more detailed follow-up through completion of the same eCRF form. Categories and examples of AEs indicating signals of possible drug abuse are provided in [Appendix 3](#) and a more comprehensive list is provided in the eCRF Completion Guidelines. (revised per Amendments 02 and 04)

- bb: The first dose of study drug will be given to the subject at the study site. Subjects will be encouraged to stay at the site for observation for at least 30 minutes following their first dose of study drug. The duration of this observation period can be extended at the investigator’s discretion, eg, if warranted by medical history or concomitant medication. (revised per Amendment 04) Visit 2 bottles are re-dispensed at Visit 3 after accountability is performed. (revised per Amendment 06)
- cc: Only for Extension Phase subjects who did not participate in optional longitudinal substudies in the Core Study but who wish to consent to optional longitudinal substudies in the Extension Phase
- dd: For subjects entering the Extension Phase only
- ee: Immunological assessments only required for subjects randomized before 07 Sep 2018
- ff: New AEs will be collected for 4 weeks post last dose and followed-up for 12 weeks, or until resolution, whichever comes first. If >4 weeks post last dose, AEs relating to study procedures will be collected only
- gg: C-SSRS to be completed if any positive responses from the Clinical Assessment of Suicidal Thinking and Behavior
- hh: For those subjects entering the Extension Phase, NPI-12 will be used if available and both NPI-10 and NPI-12 scores calculated.
- ii: Not required for those entering Extension Phase

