Appendix 5 Open-label Extension Phase (revised per Amendment 06)

Primary Objective

- To evaluate the long-term safety and tolerability of daily dosing with elenbecestat in subjects with Early Alzheimer's Disease (EAD)

Secondary Objectives

- To evaluate the long-term effects of elenbecestat on Clinical Dementia Rating –Sum Of Boxes (CDR-SB), Alzheimer's Disease Composite Score (ADCOMS), Mini Mental State Examination (MMSE), Functional Assessment Questionnaire (FAQ), Alzheimer's Disease Assessment Scale - cognitive subscale (ADAS-cog14), and ADAS-cog14 Word List (immediate recall and delayed recall)
- To evaluate the time to conversion to dementia for subjects who were not clinically staged as having dementia at Core Study baseline, based on clinical diagnosis
- To evaluate whether the treatment benefit of elenbecestat at the end of the Core Study is maintained over time in the Extension Phase

Biomarker Objectives

- To evaluate the long-term effect of elenbecestat on brain amyloid and tau levels as measured by positron emission tomography (PET) (optional substudies)
- To evaluate the long-term effect of elenbecestat on hippocampal atrophy as measured by changes in hippocampal volume using volumetric magnetic resonance imaging (vMRI)
- To evaluate the long-term effect of elenbecestat in preserving brain connectivity as measured by task-free functional magnetic resonance imaging (fMRI)
- To evaluate the long-term effect of elenbecestat on cerebrospinal fluid (CSF) t-tau, phosphorylated-tau (p-tau), and amyloid beta (A β) levels (optional substudy)
- To evaluate the long-term effect of elenbecestat on plasma amyloid (eg, A β (1-x)) levels
- To explore the long-term effect of elenbecestat on potential plasma and CSF biomarkers of AD (eg, neurofilament (NFL), visinin like protein 1 (VILIP1), human cartilage glycoprotein-39 (YKL-40), and neurogranin [Ng])

Exploratory Objectives

- To explore the long-term effect of elenbecestat on the initiation or dose increase of other Alzheimer's disease (AD) pharmacotherapies
- To explore the long-term effect of elenbecestat on the Neuropsychiatric Inventory (NPI)-10 and if available NPI-12

Eligibility Criteria

Subjects who do not meet all of the inclusion criteria will not be eligible to receive study drug.

Inclusion:

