1. Subjects who complete the 24-month Treatment Period and the 3-month Follow-up Period (Visit 15) of the Core Study, and whose Visit 15 falls within a 4-week window from the start of the Extension Phase. Subjects who discontinue study drug early are not considered to have ‘completed’ the Core Study.
2. Provide written informed consent. Subjects must, in the investigator’s judgment, have the capacity to consent (capacity to consent should be determined in accordance with applicable professional standards and local laws/regulations). In Japan, if a subject loses the capacity to consent, in the investigator's opinion during the course of the Core Study, the subject's assent should be obtained (if required in accordance with local laws, regulations, and customs) along with the written informed consent of a legal representative. (revised per Amendment 07)
3. Subjects must continue to have an identified study partner who is willing and able to provide follow-up information on the subject throughout the course of the Extension Phase.

Study Design and Plan

The Extension Phase allows eligible subjects to receive elenbecestat 50 mg for up to 24 months (2 years), or until commercial availability of elenbecestat or a lack of positive benefit-risk is determined, whichever comes first.

Subjects who are enrolled and complete the Core Study, including the 3-month Follow-up Period, will have the option to participate in the Extension Phase. Subjects who discontinue from study drug during the Core Study are not eligible to participate in the Extension Phase.

Eligible subjects may enter the Extension Phase immediately following the completion of Visit 15 of the Core Study. Subjects who are eligible to participate in the Extension Phase but who do not provide consent to transition to the Extension Phase on the day of Visit 15 may enter the Extension Phase any time within 4 weeks of Visit 15. For all subjects, assessments performed at Visit 15 will serve as baseline values for the Extension Phase.

Subjects may discontinue from the open-label study drug for any reason but are required to complete the Early Discontinuation (ED) Visit (within 7 days of last dose). In addition, subjects are required to discontinue the open-label study drug if any of the criteria specified in [Section 9.3.3](#) (Removal of Subjects from Therapy or Assessment) are met.

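### Appendix 5 does not make the first open-label dose depend on the absolute lymphocyte count

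*Protocol*

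**What the plan says.** Appendix 5 makes Extension eligibility turn on inclusion criteria alone: "Subjects who do not meet all of the inclusion criteria will not be eligible to receive study drug". It then lists three: completion of Core treatment and follow-up with a timing window, informed consent, and a continuing study partner. It lists no exclusions.

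Entry can be immediate: "Eligible subjects may enter the Extension Phase immediately following the completion of Visit 15 of the Core Study". Table 5 marks the row "Dispense study drug" at Visit 15 with a note that reads "For subjects entering the Extension Phase only". The row "Inclusion and Exclusion criteria" carries the same mark and note.

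Everyone who enters gets active drug. Section 9.1 says: "All subjects who enter the Extension Phase will be treated with elenbecestat, including the subjects who received placebo during the Core Study".

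The lymphocyte rules are elsewhere. Section 9.3.3 covers confirmation, interruption, restart and permanent discontinuation. Section 9.5.1.5.1 and note c of Table 5 cover low counts found at Visits 14 and 15.

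**The concern.** The Core Study barred entry at a lymphocyte count below the lower limit of normal or 800/mm³, whichever is higher (Section 9.3.2, criterion 9). Former placebo subjects take elenbecestat for the first time in the Extension, yet no lymphocyte limit is stated for that first dose. Section 7.1 reports some CD4 reduction by Day 15 at 50 to 100 mg, a range that includes the 50 mg study dose. A subject could therefore start the drug at a count at which the protocol would stop it in someone already taking it. What is at stake is subject safety. Extension safety data are summarized descriptively, so no test or estimate depends on this.

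**Working it through.** There is no stated figure to reproduce. The check is whether any rule blocks a first open-label dose at a known count below 800/mm³.

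1. **Extension entry criteria (Appendix 5).** Three inclusion criteria; none is a laboratory condition; no exclusions.
2. **Low count at Visit 14 or 15 (Section 9.5.1.5.1; Table 5, note c).** The stated action is re-measurement every 4 weeks until the count resolves or a cause unrelated to drug is confirmed. Nothing is said about withholding open-label drug.
3. **Count above 800/mm³ (Section 9.3.3).** This is a condition for restarting drug after an interruption for a confirmed low count. It is not worded as a condition for a first dose.
4. **Extension two-event rule (Section 9.3.3).** It counts events from Visit 16 onwards, so low counts at Visits 14 and 15 do not contribute.
5. **Appendix 5's reference to Section 9.3.3.** It invokes those criteria for discontinuing open-label drug, not for entry.
6. **Core lymphocyte exclusion (Section 9.3.2).** It applies to results obtained during Screening. The Synopsis heads the list as belonging to the Core Study, and criterion 19 excludes anyone who took part in an elenbecestat study. The Core list therefore cannot be applied literally at Visit 15.

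Timing, using the nominal days in Table 5:

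- Visit 14 is Day 757 and Visit 15 is Day 813, so the gap is 813 − 757 = 56 days. A Visit 14 result would normally be known before dispensing.
- 4-weekly repeats after a low Visit 14 count fall on 757 + 28 = Day 785 and 785 + 28 = Day 813.
- The 4-week entry allowance ends on 813 + 28 = Day 841. If the first low count is at Visit 15, the next 4-weekly measurement also falls on Day 841, the last day of the allowance.

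The clearest case follows. A subject has a first low count at Visit 15, the result comes back, and the subject enters later in the allowance. There is one known low count, the only expressly required re-measurement may not yet be due, and no rule holds the drug.

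The age of the result is not the problem. Section 9.1.1.1 accepts Tier 1 to 3 screening results for 96 days, and a Visit 14 result is 56 days old at Visit 15.

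**The case against.** The strongest reply is that Section 9.3.3 already protects these subjects. Its monitoring and 5-day retest are not limited to the Treatment Period, so they can be read as adding to the 4-weekly rule. Under Section 9.4.6 the site stays blinded through follow-up. Every entrant has been on blinded study drug, so a site holding a known low count could reasonably apply the restart condition to all of them. This weakens the gap but does not close it: the plainest reading still ties restart to a preceding interruption, and a retest alone does not withhold a dose.

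The Core two-event rule also matters. A reader might infer that a subject low at Visit 14 and again at the Day 785 repeat is certain to be dosed. The documents do not support that. Section 9.3.3 applies the rule to the Core Study as a whole, which would permanently discontinue such a subject if the two counts are confirmed and treated as separate events. The Synopsis limits the rule to Core Study treatment, and neither text says whether one persistent low count is one event or two. A single known low count is reached by neither version.

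Other safeguards stand. Investigators must review laboratory findings and may withdraw a subject for safety at any time, and hematology is drawn at Visits 14, 15 and 16. On harm, Section 7.1 links possible infection risk to CD4 and CD8 reductions at 200 and 400 mg, not 50 mg, and reports that lymphocyte effects resolved gradually between Day 20 and Day 35 after dosing ended on Day 14.

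**Conclusion.** The point holds in a narrow form. Followed literally, the protocol lets a subject with a known count below 800/mm³ be dispensed elenbecestat. Severity is low and the remedy is a cheap improvement. The documents give no rate of low counts during follow-up, so the number affected is unknown.

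Three stronger readings should not be drawn:

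- **A fixed length of exposure.** One could compute time to interruption as T + up to 5 + T days, where T is laboratory turnaround per test: up to 5 days at T = 0 and up to 11 at T = 3. T is an assumption that the documents do not supply, and the conclusion does not rest on it.
- **A missing exclusion list.** The "Inclusion and Exclusion criteria" row at Visit 15 has no Extension exclusions to refer to, but that shows a label needing correction, not that particular Core exclusions were meant to be repeated.
- **Lapsed medication restrictions.** The look-back windows in Section 9.4.7 are anchored to randomization or Screening. However, the Synopsis heads the restrictions as covering both phases and Appendix 5 applies Section 9.4.7 to the Extension. The text is unclear on the follow-up months, not demonstrably wrong.

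**What to change.** Add to Appendix 5, for all entrants so that blinding is not an issue:

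- Do not dispense open-label drug while the most recent available lymphocyte count (Visit 14, any repeat, or Visit 15 if the result is back) is below 800/mm³.
- Require a repeat above 800/mm³ first, drawn on the 5-calendar-day rule of Section 9.3.3 and not on the 4-weekly schedule.
- State that the 4-week entry allowance may be used for this. The point needs saying because Section 9.1 opens the allowance to subjects "who do not transition to the Extension Phase on the day of Visit 15 may enter the Extension Phase any time within 4 weeks" of that visit, whereas Appendix 5 describes those "who do not provide consent to transition to the Extension Phase on the day of Visit 15 may enter the Extension Phase" within the same period, which ties it to late consent.

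Correct the Table 5 row label at Visit 15 so that it refers to the Extension inclusion criteria.

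The cost is an amendment to wording. Hematology at Visits 14 and 15 is already scheduled, and Section 9.5.1.5.3 already allows a split sample for a local read where there is a safety concern. A few entrants would face a short delay or an extra draw, and any whose count stays low through the allowance would not enter.
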